5.2.2 Pretreatment visit

Patients will be hospitalized on the evening before the day of the pretreatment angiography. They will be discharged approximately 24 hours after the intervention unless complications occur. The screening visit can coincide with the pretreatment and treatment visit, if so, duplicate procedures need not be performed. If the treatment is shortly after the pretreatment, the hospital stay can be extended for the duration of that visit. During this visit, the following must be documented and reviewed as a part of the study:

- Inclusion and exclusion criteria
- Physical examination (incl. vital signs)
- Pregnancy test for women of childbearing age
- WHO performance assessment
- Concomitant medication
- Monitoring of occurrence of (serious) adverse events
- Laboratory examination type A (blood)
- Pretreatment angiography, administration of ^{99m}Tc -MAA
- ^{99m}Tc -MAA SPECT/CT

On day 0, the patient is subjected to an angiography of the upper abdominal vessels. At least the celiac axis and superior mesenteric artery are visualised, followed by coiling of relevant vessels, especially branches of the celiac axis supplying non-target organs. This procedure will be performed by a skilled and trained interventional radiologist. The catheter is introduced using the Seldinger technique. Prior to the procedure the patient is offered a tranquilizer. Premedication consists of proton pump inhibitors (pantoprazol 1 dd 40 mg), starting at the day of the intervention. Proton pump inhibitors are prescribed to the patients to be used until 3 months post ^{166}Ho -RE.

After successful angiography and coiling of relevant vasculature, a dose of ^{99m}Tc -MAA will be administered. The patient is subjected to scintigraphy to determine the distribution. Both planar imaging of the thorax and abdomen will be performed, as well as SPECT/CT of the abdomen. The thorax and abdomen images will be evaluated qualitatively and the images of the thorax will be evaluated quantitatively (region of interest analysis for lung shunting) as well. Extrahepatic deposition of activity is a contra-indication for administration of ^{166}Ho -PLLA-MS. If the extrahepatic deposition of ^{99m}Tc -MAA cannot be corrected by means of available radiological interventional techniques, the patient will not be eligible to receive a scout or therapy dose of ^{166}Ho -PLLA-MS. If the lung shunt fraction exceeds 20% of the dose of ^{99m}Tc -MAA, the patient will not be eligible to receive a scout or therapy dose of ^{166}Ho -PLLA-MS.

5.2.3 Treatment visit

The second intervention takes place around 1 week after the first intervention but not later than 3 weeks after. Patients will be hospitalized on the evening before the day of treatment. They will be discharged approximately 24 hours after the intervention unless complications occur. During this visit, the following must be documented and reviewed as a part of the study:

- Inclusion and exclusion criteria
- Physical examination (incl. vital signs)
- WHO performance assessment
- Concomitant medication
- Pretreatment MRI
- Treatment angiography, administration of scout dose of ^{166}Ho -PLLA-MS
- Post scout dose SPECT/CT

- Post scout dose MRI or post scout- and post therapy dose ^{166}Ho -PET/CT
- Treatment angiography, administration of therapy dose of ^{166}Ho -PLLA-MS
- Post treatment MRI
- Monitoring of occurrence of (serious) adverse events
- Collecting of 24-hours urine for holmium content (using either a condom-catheter or an Foley catheter)
- Laboratory examination type A and C (blood and urine)
- Radiation exposure rate

Prior to the procedure, the patient is offered a tranquilizer and a Foley catheter is inserted or a condom-catheter is applied for 24-hours urine collection. If a Foley catheter is used, the patient will receive a single dose of antibiotics 3 hours post ^{166}Ho -RE (therapy dose). An experienced interventional radiologist will administer the scout dose of ^{166}Ho -PLLA-MS through a catheter inside the hepatic artery at the position as planned during the first intervention. At the end of this angiography, the vascular sheath will remain in situ (femoral artery). This sheath will be used for the treatment angiography later that day. The vascular access site will be covered with a sterile patch. In addition, NaCl 0.9% under pressure will be connected to the sheath to prevent from clot formation. The patient will remain in supine position in his/her bed and will be transferred to the MRI / PET and SPECT scanners. In order to detect inadvertent administration to the lungs or other non-target organs (e.g. stomach, duodenum, pancreas) scintigraphy will be performed after administration of the scout dose of ^{166}Ho -PLLA-MS to assess its distribution. Both planar imaging of the thorax and abdomen will be performed, as well as SPECT of the abdomen. If the ^{166}Ho -PLLA-MS scout dose SPECT is suspect for extrahepatic deposition, after a week a second $^{99\text{m}}\text{Tc}$ -MAA procedure will be started. In this procedure the blood vessels that probably cause the extrahepatic deposition will be identified if possible. Based on the findings, the interventional radiologist might adapt the catheter position and/or coil the culprit extrahepatic vessels. In case the second $^{99\text{m}}\text{Tc}$ -MAA SPECT does not show extrahepatic deposition, a new ^{166}Ho -PLLA-MS scout dose will be administered. In case this second ^{166}Ho -PLLA-MS scout dose SPECT does not show extrahepatic deposition the ^{166}Ho -PLLA-MS therapy dose will be given. If again extrahepatic ^{166}Ho -PLLA-MS scout dose deposition occurs, the treatment will be terminated.

In order to obtain detailed information on the distribution of the ^{166}Ho -PLLA-MS, **either** MRI will be performed after the scout dose **or** ^{166}Ho -PET/CT will be performed both after the scout dose and the therapy dose. ^{166}Ho -PET/CT will be performed in the 1st – 6th patient that receive ^{166}Ho -RE. In the 7th – 12th patient, ^{166}Ho -PET/CT will not be performed. Instead, these patients will receive an MRI of the ^{166}Ho -MS scout dose. After the first 12 patients, patients will either receive an MRI of the ^{166}Ho -MS scout dose or a ^{166}Ho -PET/CT scan of the scout dose and a ^{166}Ho -PET/CT of the therapy dose. MRI will be performed after the therapy dose in all patients of the HEPAR II trial.

The MRI after the scout dose will be a non-contrast enhanced MRI of limited duration (less than 15 minutes acquisition time). The ^{166}Ho -PET/CT will be performed with a low-dose, non-contrast enhanced CT scan for anatomical reference, and will be of limited duration (approximately 30 minutes). Because the 1st – 6th patient will undergo different imaging than the 7th – 12th patient, there are two versions of the patient information letter in which either ^{166}Ho -PET/CT or ^{166}Ho -MS scout dose MRI is embedded.

The target liver absorbed dose is fixed to 60 Gy and, therefore, the total amount of radioactivity of the therapy dose varies with the liver weight (see chapter 6.5, Table 4). An experienced nuclear medicine physician will administer both the scout and therapy dose assisted by the interventional radiologist.

5.2.4 Visit week 1

This visit will take place at the outpatient clinic. During this visit, the following must be documented and reviewed as a part of the study:

- Post therapy scintigraphy (scan will be acquired when the administered dose will have decayed to 500 megabecquerel (MBq) or less, which will take around 3-5 days, depending on the administered dose)
- QoL

5.2.5 Visit week 3

This visit will take place at the outpatient clinic. During this visit, the following must be documented and reviewed as a part of the study:

- Physical examination (incl. vital signs)
- WHO performance assessment
- Concomitant medication
- Monitoring of occurrence of (serious) adverse events
- Laboratory examination type B (blood)

5.2.6 Visit week 6

These visits will take place at the outpatient clinic. During these visits, the following must be documented and reviewed as a part of the study:

- Physical examination (incl. vital signs)
- WHO performance assessment
- Concomitant medication
- QoL
- Monitoring of occurrence of (serious) adverse events
- Laboratory examination type B (blood)

5.2.7 Visit week 9

This visit will take place at the outpatient clinic. During this visit, the following must be documented and reviewed as a part of the study:

- Physical examination (incl. vital signs)
- WHO performance assessment
- Concomitant medication
- Monitoring of occurrence of (serious) adverse events
- Laboratory examination type B (blood)

5.2.8 Visit 3 months

This visit will take place at the outpatient clinic at 3 months post treatment \pm 7 days. During this visit, the following must be documented and reviewed as a part of the study:

- Physical examination (incl. vital signs)
- WHO performance assessment
- Concomitant medication
- QoL
- Monitoring of occurrence of (serious) adverse events
- Laboratory examination type A (blood)
- PET/CT, MRI

5.2.9 Visit 6, 9, and 12 months

This visit will take place at the outpatient clinic at 6, 9, and 12 months post treatment \pm 14 days. During this visit, the following must be documented and reviewed as a part of the study:

- Physical examination (incl. vital signs)
- WHO performance assessment
- Concomitant medication
- QoL
- Monitoring of occurrence of (serious) adverse events
- Laboratory examination type A
- PET/CT, MRI

5.3 Holmium content

Pooled urine samples will be collected from -5-0 hours (the beginning of the safety dose angiography until the end of the therapy dose angiography), 0-3 hours (end of therapy dose angiography until 3 hours afterwards), 3-6 hours, and 6-24 hours following therapy dose administration. The date and time of the start and the end of the collection period, and whether the collection was complete or not, will be noted in the E-Case Report Form (CRF). Measurement of holmium content in urine and blood will be performed. The date and the time of measurement and the results will be reported in the E-CRF.

During the hospitalization for treatment (at $t = 0, 3, 6,$ and 24 hours following ^{166}Ho -PLLA-MS administration) blood will be drawn for measuring the holmium content in the blood. $T=0$ measurement is performed when the patient has returned to the ward after treatment angiography.

5.4 Laboratory examinations

Blood samples for safety parameters will be taken using an indwelling canula or by single vein puncture. During the follow-up visits with the investigator, blood samples for safety parameters will be drawn by a research nurse and delivered to the Laboratory of Clinical Chemistry and Haematology (see Table 3).

5.5 Radiation exposure rate

During the hospitalization for treatment, the radiation exposure rate will be measured at $t = 0,$ and 24 hours from 1 meter distance (see Table 2). $T=0$ measurement is performed when the patient has returned to the ward after treatment angiography.

5.6 Use of co-medication / prophylactic measures

All patients that are eligible for the experimental treatment will receive proton pump inhibitors (pantoprazol 1 dd 40 mg) starting the day before the catheterisation, which will be continued for 6 weeks.

All patients that are eligible for the experimental treatment will receive anti-emetic drugs (ondansetron i.v. 8mg) and prevention of contrast allergy (dexamethason 16mg p.o. and 10mg i.v. and clemastine 1mg p.o.) prior to catheterisation.

During the vascular intervention the patient will receive heparin (1000 IU/ml in saline, up to 5000 IU), to avoid the formation of thromboembolism during the intervention.

The vascular intervention will be performed under x-ray guidance. To be able to visualise the blood vessels during the procedure, a non-ionogenic x-ray contrast agent (jodixanol, Visipaque[®]) will be administered to the patient.

Should women of childbearing age require microsphere therapy, non-pregnancy needs to be ascertained prior to treatment. Therefore, proper contraceptive measures should be used, such as the birth control pill.

As a prophylactic measure for thromboembolic events, all patients will be provided with pressure stockings at the day of each angiography. Patients will be advised to wear these pressure stockings until the end of hospitalization or until the moment that patient is able to mobilise.

After the angiography, when the urinary catheter is removed, patients receive a single gift of amoxicillin/clavulanic acid (1000/200mg i.v.) for prevention of urinary tract infections.

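### Sections 5.2.2, 5.2.3 and 5.6 prescribe conflicting schedules for the acid suppressant and for the single antibiotic dose, so the prophylaxis given depends on which section is followed

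*Protocol*

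**What the plan says.** **Acid suppression.** Protocol section 5.2.2, describing the visit for the pretreatment angiography, reads: "Premedication consists of proton pump inhibitors (pantoprazol 1 dd 40 mg), starting at the day of the intervention". It then sets the end: "Proton pump inhibitors are prescribed to the patients to be used until 3 months post" radioembolization. Section 5.6, which applies to all patients eligible for the experimental treatment, names the same drug at the same daily dose, "starting the day before the catheterisation, which will be continued for 6 weeks". It does not say which catheterisation it means. There are two, and section 5.2.3 gives the interval: "The second intervention takes place around 1 week after the first intervention but not later than 3 weeks after".

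**Antibiotic.** Section 5.2.3 reads: "If a Foley catheter is used, the patient will receive a single dose of antibiotics 3 hours post" radioembolization, with the therapy dose named as the reference. Section 5.6 instead says that after the angiography, "when the urinary catheter is removed, patients receive a single gift of amoxicillin/clavulanic acid", to prevent urinary tract infection. Section 5.2.3 allows either a Foley or a condom catheter for the urine collection. Section 5.6 does not distinguish between them.

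**The concern.** These are current, operative instructions to ward and clinic staff, and the document contains no statement that reconciles them or gives one section precedence. A team that follows one section departs from the other. The first conflict reaches every treated patient (planned 30 to 48). The second reaches every patient with a Foley catheter, and for patients with a condom catheter it is unclear whether the antibiotic applies at all.

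The protocol itself connects these measures to risks. Section 7.2.1 puts peptic ulceration at under 10% of patients undergoing radioembolization, section 11.3.2 says a urethral catheter may cause infection, and section 5.6 gives the antibiotic for that reason. Toxicity is a secondary endpoint (section 8.1.2), and the data are meant to support a CE marking application (section 12.8). In a one-group study there is no control arm against which the effect of varying prophylaxis could be separated from the effect of the device.

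**Working it through.** The protocol states no figure of its own to reproduce, so the check sets the sections side by side and puts them on a common clock.

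**Acid suppression, days of cover after radioembolization**

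Inputs: end at 3 months after treatment (5.2.2), taken as about 91 days; 6 weeks = 6 × 7 = 42 days, counted from the day before a catheterisation (5.6); treatment about 7 and at most 21 days after the first angiography (5.2.3).

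| Reading | Days after treatment | Gap to 5.2.2 |
|---|---|---|
| 5.2.2 | about 91 | – |
| 5.6, treatment catheterisation meant | 42 − 1 = 41 | 91 − 41 = 50 |
| 5.6, first angiography meant, treatment 7 days later | 42 − 1 − 7 = 34 | 91 − 34 = 57 |
| 5.6, first angiography meant, treatment 21 days later | 42 − 1 − 21 = 20 | 91 − 20 = 71 |

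The post-treatment durations therefore differ by about 50 to 71 days. As a ratio, that is from 91/41 ≈ 2.2 to 91/20 ≈ 4.5.

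**Acid suppression, start**

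Section 5.2.2 starts on the day of the first angiography. If 5.6 means that same procedure, its start is one day earlier. If 5.6 means the treatment catheterisation, its start falls 7 − 1 = 6 to 21 − 1 = 20 days later than under 5.2.2. The direction of the difference, as well as its size, depends on the undefined word.

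**Antibiotic**

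Section 5.2.3 fixes the dose at 3 hours after the therapy dose. Section 5.6 ties it to catheter removal, for which no section states a time. The catheter is placed for a 24-hour urine collection (5.2.3), and section 5.3 has the last collection interval running from 6 to 24 hours after the therapy dose. If the catheter stays for that collection, removal comes at about 24 hours, and the gap is 24 − 3 = 21 hours. Removal at 3 hours would cut off the two later intervals (3–6 and 6–24 hours), so the two instructions do not coincide under the protocol's own collection plan. Giving the antibiotic at both times is not a way out, because each section specifies a single dose.

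**The case against.** The strongest case on the other side concerns consequence. A reader might infer that patients' protection against ulcer and infection will differ between the two schedules. The documents do not support that. They contain no data relating either risk to the duration or timing of prophylaxis, so only the prescribed prophylaxis is shown to differ. This stands.

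A reader might also compare 6 weeks with about 13 weeks and call it a two-fold difference with a one-day difference in start. Those figures mix two clocks, one running from treatment and the other from the day before a catheterisation, and they assume which catheterisation is meant. The ranges above replace them. The 21 hours is likewise an inference from the urine collection and is not a protocol figure.

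The effect on the safety data is also limited:

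- The trial is single-centre, so there is no divergence between sites, although staff within the centre may still differ.
- Concomitant medication is documented at pretreatment, at treatment, at weeks 3, 6 and 9 and at 3 months (sections 5.2.2 to 5.2.8), so the prophylaxis actually given should be recoverable.
- Toxicity is reported as counts and percentages in one group (section 10.2), so no comparison between arms can be biased.
- The monitoring guidance in section 8.4 singles out bilirubin and factor V. Other grade 3–4 events fall under a general 50% guide.

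All of this lowers the weight of the point. None of it makes the sections compatible.

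**Conclusion.** The contradiction holds on both counts. Sections 5.2.2 and 5.6 cannot both be followed for the acid suppressant, and sections 5.2.3 and 5.6 cannot both be followed for the antibiotic.

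The acid-suppression gap after treatment is about 50 days if 5.6 refers to the treatment catheterisation, and about 57 to 71 days if it refers to the first angiography. This rests on 3 months being about 91 days and on the 1-to-3-week interval in section 5.2.3. The antibiotic gap is about 21 hours, provided the catheter stays in place for the full collection.

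The effect on ulcer or infection rates cannot be computed from the documents and is not claimed. The primary endpoint, stopping boundaries, type I error and power are untouched. The point is an inconsistency in supportive care that bears on conduct and on reading the safety data, and it should be corrected because it governs what patients are given.

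**What to change.** The clinical team must reconcile sections 5.2.2, 5.2.3 and 5.6. For the acid suppressant, settle three items: the start, the catheterisation it is counted from, and the duration. For the antibiotic, settle two: its timing and which catheter users it covers. State each schedule once and have the other section cross-refer to it. No position is taken here on which schedule is right.

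The cost is a few lines of wording in an amendment. It changes no endpoint, sample size or analysis.

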5.7 Escape medication

All escape medication mentioned below is equal to the standard escape medication for treatment with ⁹⁰Y-RE.

Patients are offered intravenous analgesics (morphine 7.5 mg – 15 mg/24 h) prior to the procedure. Patients may receive oral analgesics (paracetamol up to 4000 mg/24 h) for relief of fever and pain after the administration of microspheres. To reduce nausea and vomiting, patients will receive anti-emetics (ondansetron up to 3 dd 8 mg) during the first 24 hours after administration of microspheres. In the case of persisting nausea, metoclopramide (up to 300 mg/24 h) will be used.

The vascular contrast agent jodixanol (Visipaque[®]) can cause renal insufficiency in poorly hydrated patients. Therefore, patients will be hydrated according to the CBO-directive “Richtlijn Voorzorgsmaatregelen bij jodiumhoudende contrastmiddelen”, page 23-26 (see Appendix VI).

Inadvertent shunting of microspheres to non-target organs, including the lungs, stomach, pancreas, duodenum and the gall bladder, can be associated with serious side effects. To reduce toxicity of the radioactive microspheres in this case, amifostine (Ethyol[®], up to 200 mg i.v./m² for 7 days) can be administered.

In case patients with neuroendocrine tumours receive this experimental treatment, the release of neuroendocrine factors may give rise to the so called ‘carcinoid syndrome’ (see 7.1.8). This syndrome can be prevented to some extent with octreotide (300 µg i.v./24 h).

6. INVESTIGATIONAL MEDICAL DEVICE

6.1 Name and description of investigational medical product

The device under investigation comprises radioactive particles dedicated for treatment of hepatic malignancies. The particles, called microspheres, contain the radionuclide holmium-166, which emits gamma rays (81 kilo electron volt (keV)) and high-energy (1.8 mega electron volt (MeV)) beta particles. The beta particles are responsible for the therapeutic effect of the device, the gamma ray can be used for nuclear imaging purposes.

Liver metastases are preferably supplied by the hepatic artery. This selective vascularisation allows the use of the hepatic artery for selective administration to the metastases without compromising hepatic flow by the portal vein. The microspheres are locally administered by means of selective catheterisation of the hepatic artery by a trained intervention radiologist.

6.2 Animal studies

Several animal studies have been performed with ¹⁶⁶Ho-PLLA-MS. These studies were aimed to get insight into the toxic effect, the method/technique of administration, efficacy, safety and in vivo stability of the microspheres. The studies have been performed on rats, rabbits, and pigs. The animal studies showed positive results. An overview and summary of the animal studies performed is given in the Investigational Medical Device Dossier (IMDD, page 13, 18 and Appendix 6).

6.3 Clinical studies

In the HEPAR I trial, 15 patients with liver metastases from miscellaneous primary cancers have received radioembolization with escalating doses of ¹⁶⁶Ho-PLLA-MS (20-40-60-80 Gy). Cohorts consisted of 3-6 patients. The treated patients with liver metastases consisted of 7 patients with metastases of ocular melanoma, 5 with metastases of colorectal carcinoma, 2 with metastases of cholangiocarcinoma and 1 with metastases of breast cancer. The 20 Gy-cohort was extended to 6 patients because one patient had developed a pulmonary embolism post ¹⁶⁶Ho-RE. This serious adverse event was ascribed to the lengthy procedure in this patient. The last cohort (80 Gy) consisted of 3 patients and was stopped because of dose limiting toxicity in two patients, as was prospectively described in the study protocol. The other two cohorts (40 Gy and 60 Gy) comprised 3 patients each.

Clinical toxicity in the first 3 cohorts consisted mainly of symptoms belonging to the post embolization syndrome (PES)[29]. PES comprises fatigue, nausea, abdominal pain, fever, vomiting and/or anorexia, and is a known phenomenon in radioembolization treatment. These symptoms were transient in all cases and well-controlled by outpatient medication. Laboratory toxicity was mild except for expected grade 3 liver enzymes toxicity and grade 3 haematological toxicity. Overall, treatment was well tolerated by the patients in the first 3 cohorts (20 Gy – 60 Gy) and the toxicity profile was very similar to the toxicity which is encountered in patients treated with ⁹⁰Y-RE [29-31]. In the 80-Gy cohort, however, treatment was considerably less well tolerated. Patients had more complaints of abdominal pain and nausea. These symptoms were more severe and lasting longer than the clinical toxicities encountered in the previous cohorts. Furthermore, laboratory toxicity was more severe and in certain cases progressive with a suspected radiation induced liver disease (RILD) in one patient. Liver toxicity is to some extent intended in radioembolization given the 5-mm reach of the beta emitting holmium. Furthermore, lymphocyte- (up to grade 3), leukocyte- (up to grade 3) and platelet counts (up to grade 4) transiently decreased. These adverse events are most probably caused by activation of hepatic stem cells in the bone marrow due to liver damage [27]. These symptoms are suspected to be related to the higher radiation dose instead of an embolic effect of treatment because the amount of microspheres was equal in

all cohorts. As a consequence, dose limiting toxicity was reached in the 80 Gy-cohort and the decision was taken to stop the study and continue with 60 Gy as a target dose for the HEPAR phase II study. A listing of all adverse events encountered in the HEPAR I trial is given in Appendix XIII. This study was not designed to demonstrate efficacy of ^{166}Ho -RE, but a number of partial remissions and stable disease were observed.

A summary of the HEPAR I trial is given in the IMDD (page 14).

